### Human laboratory methods for Phase II medication screening

As emphasized in the "Rosetta stone" approach to drug development  and the NIAAA medication development strategy , human laboratory trials play a pivotal role in drug development by providing a bridge from preclinical studies and full-scale Phase II/III trials . Importantly, laboratory studies can expedite drug development by providing an efficient, cost-effective, and rigorous option for "early-Phase II" medication screening, thereby informing priorities for larger and more costly randomized trials. We recently published meta-analytic evidence that laboratory studies of naltrexone, when examined in aggregate, yield conclusions highly comparable to the aggregate data from large-scale randomized trials, reinforcing the notion that laboratory trials offer a valid approach for estimating medication effects . Other advantages of laboratory trials include the ability to study putative treatment mechanisms under controlled conditions, and the ability to quickly generate initial data on drug tolerability in the clinical population of interest .

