Participants will complete the following questionnaires, which will be programmed in RedCap software. A **Demographic Screening Questionnaire** will assess basic demographic factors (e.g., age, education, income). A **Locator** collects contact information for three to five individuals who can be contacted if a participant is unable to be reached by study staff for follow-up visits. Other baseline measures (to be administered by computer using RedCap software) will include the **Alcohol Use Disorders Identification Test** , **Self-Report of the Effects of Alcohol Questionnaire (SRE)** , **Fagerström Test of Nicotine Dependence** , and the **Nicotine Dependence Syndrome Scale** . Baseline measures that will be repeated at subsequent visit will include the **TLFB**, the **Penn Alcohol Craving Scale (PACS)** and **Tiffany Questionnaire of Smoking Urges (TQSU)** , the **Yale Craving Scale**, and the **Minnesota Nicotine Withdrawal Scale** . To assess potential medication effects on changes in motivation and self-efficacy for resisting alcohol/cigarettes, we will use alcohol and smoking **Contemplation Ladder** items, alcohol and cigarette **Abstinence Self-Efficacy (AASE and SEQ)** and **Inventory of Drinking Situations** scales . Given lorcaserin's effect on food intake, changes in appetite will be assessed with the **Three Factor Eating Questionnaire**  and the **Reward-Based Eating Drive Scale** . The **PROMIS** Depression scale and Beck Depression Inventory-II will be administered to assess potential depressive symptoms. If participants report suicidal ideation, standard MRN protocols will be followed, including further assessment of the participant by medical staff and/or the PI, offering a referral, and following up with the participant. The **Wechsler Test of Adult Reading (WTAR)** will be used to estimate intelligence. During the medication phases, side effects will be assessed with the **SAFTEE** questionnaire  and an **Adverse Events Checklist** .

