**Follow-up Visits 1 and 2.** At each of two follow-up visits, participants will report to MRN in the morning, having received instructions to abstain from alcohol and recreational drugs for 24h, and from food for 4 hours. Upon arrival participants will provide breathalyzer and expired CO readings, as well as repeat measures of body weight and vitals (HR, BP). Participants will also repeat the CIWA assessment and will complete a blood draw (up to 20 ml) at each session which may only be used for determining the level of medication metabolites present (i.e., a measure of adherence). Blood draws will be performed by trained research staff. Participants will take that day's morning pill under observation. Next, participants will be given the first of three 15-minute smoking breaks (to ensure that participants are not nicotine-deprived during testing), which is a common approach in laboratory studies. Smoking breaks will occur in a ventilated room, which has been used for prior smoking studies. Participants will also be asked to complete short questionnaires before and after the break (measuring craving and subjective effects, see measures above). After the break, participants will consume a standardized snack, followed by self-report and computerized assessments, including interim assessments of substance use and craving, side effects and adherence, and computer-based impulsivity tasks (see Measures). Next, participants will complete the medical assessment with the study medical staff, including a weight measurement and a urine screen (to detect riboflavin as a measure of adherence). Assuming no medical contraindications, participants will proceed to begin a previously validated alcohol self-administration procedure, described below.

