**Table 1. Study Measures**

VISIT	MEASURE/PROCEDURE	TIME (MINS)
Screening	Consent	30
	Breath alcohol test	2
	Urine drug screen	5
	Urine pregnancy test (females)	5
	Expired CO	2
	TLFB	30
	SCID	60
	CIWA	5
	The Wechsler Test of Adult Reading (WTAR)	10
	Blood draw	5
Medical screen (may occur on different day than screening)	Physical Exam	10
	Medical History	15

VISIT	MEASURE/PROCEDURE	TIME (MINS)	
depending on availability)	EKG	20	
	CIWA	5	
Baseline/First Dispensing Visit	Demographics form	5	
	Locator form	10	
	CIWA	5	
	AUDIT	2	
	SRE	2	
	FTND	1	
	NDSS	3	
	TLFB	10	
	PACS	1	
	TQSU	1	
	Yale Craving Scale	5	
	Contemplation Ladder	1	
		Three Factor Eating Questionnaire	3
		Simplified Nutritional Appetite Questionnaire	2
		Reward Based Eating Drive Scale	2
		PROMIS Depression/BDI-II	4
		Stop signal	10
		CPT	10
		Reward Responsiveness Test	15
		Monetary Choice Questionnaire	2
		Alcohol Purchase Task	2
		Cigarette Self-efficacy (SEQ)	1
		Alcohol self-efficacy (AASE)	1
		Cigarette Purchase Task	2
		Inventory of Drinking Situations (IDS-30)	5
		Food delay discounting task	4
	SAFTEE	10	
Between Baseline & Follow up visit 1	Call participant on days 2 and 4 to assess side effects SAFTEE/Adverse Effects Checklist	10	
Follow up visit 1 (including alcohol consumption session)	Expired CO/Breath Alcohol	4	
	CIWA	5	
	Yale Craving Scale	5	
	Blood draw	5	
	Take dose of medication	2	
	Smoking break	15	
	TQSU	1	
	MNWS	1	

VISIT	MEASURE/PROCEDURE	TIME (MINS)
	PACS	1
	TLFB	10
	SAFTEE/Adverse Effects Checklist	8
	Cigarette Self-efficacy (SEQ)	1
	Alcohol self-efficacy (AASE)	4
	Stop signal	10
	CPT	10
	Reward Responsiveness Test	15
	Monetary Choice Questionnaire	2
	Alcohol Purchase Task	2
	Cigarette Purchase Task	2
	Food delay discounting task	4
	Weight	1
	Three Factor Eating Questionnaire	3
	Reward-Based Eating Drive Scale	2
	PROMIS Depression/BDI-II	4
	Simplified Nutritional Appetite Questionnaire	2
	Medical check-in	5
	Urine test (pregnancy, drugs, riboflavin)	5
	Priming drink + absorption	35
	TQSU	1
	BAES	1
	AUQ	1
	DEQ	1
	Ad libitum drinking session	120
	Smoking break	15
	TQSU	1
	BAES	1
	AUQ	1
	DEQ	1
	Alcohol Purchase Task	2

VISIT	MEASURE/PROCEDURE	TIME (MINS)
	Cigarette Purchase Task	2
	Smoking break	15
Washout	7 days with no medication	
	TLFB	10
	Dispense 2 nd medication	10
	Simplified Nutritional Appetite Questionnaire	2

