Pharmacokinetic and pharmacodynamic profile. According to the prescriber's brochure, lorcaserin reaches peak plasma concentrations in 90 - 120 minutes after oral dosing. Steady-state plasma levels are achieved after 3 days of twice-daily dosing, and the plasma half-life is roughly 11 hours.

Human studies have demonstrated that lorcaserin distributes to cerebrospinal fluid and the CNS. Lorcaserin is metabolized via multiple enzymatic pathways in the liver and excreted primarily (92%) in urine. Its metabolites shows no activity at 5-HT receptors.

*Selected dosage and medication duration.* The current study will use the FDA-approved dosage of 10mg twice- daily (BID). This dosage was used in the recent smoking cessation trial noted above. We will use a 7-day medication schedule because a) this allows more than adequate time to reach steady-state plasma levels, and b) this time frame allows us to capture short-term changes in naturalistic smoking/craving in this sample. Of note, recent data suggest that lorcaserin has acute effects on reducing nicotine intake when administered 15 min. prior to testing , suggesting that short-term medication exposure is adequate to observe effects on addiction-related outcomes. In addition, the first neuroimaging study of lorcaserin found differences in neural reactivity to hedonic food cues following one week of treatment .

**Questionnaire and Interview Assessments.** There are potential psychological risks associated with assessment procedures. Participants may find the battery of psychiatric and psychological assessments tedious or intrusive. Participants may experience discomfort resulting from questions about personal histories or substance use patterns.

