**Participation in Alcohol Administration Sessions.** Other potential risks include those related to participation in alcohol administration sessions. For example, it is possible that participants may experience dizziness/nausea from drinking during these visits, or during smoking breaks. Our group has considerable experience with alcohol administration and self- administration procedures , and the safety precautions required in these studies. These procedures will follow the NIAAA recommended guidelines for administering alcohol to human subjects (<https://www.niaaa.nih.gov/Resources/ResearchResources/job22.htm>). In particular, we have taken measures to protect against ethical concerns by excluding treatment-seekers or those engaged in an active quit attempt.

**Confidentiality/Privacy.** Risks from potential breaches of confidentiality include invasion of privacy, as well as social and economic risks. Economic risks include alterations in relationships with others that are to the disadvantage of the subject, and may involve embarrassment, loss of respect of others, labeling with negative consequences, or diminishing the subject's opportunities and status in relation to others. There is also a risk of breach of data confidentiality (uncommon).

**Risks Related to DNA Collection.** The purpose of collecting saliva for DNA in this study is to allow secondary analyses to examine whether medication effects might be different according to certain genetic factors. The main aim of this analysis will be to examine the *CYP2A6* gene, which is related to nicotine metabolism. These analyses may also focus on genetic factors potentially associated with drug use or related behaviors, such as impulsivity. Potential risks associated with DNA collection involve potential identification, and there may be risks with genetic (DNA) tests that are as yet unknown. Genes may be shown at some point in the future to be related to mental illnesses or tendency to addiction. Samples will be labeled with participant ID only, and analyzed at an outside laboratory. Samples will be destroyed upon completion of the analyses. We will not conduct any whole genome sequencing of the DNA samples. Additionally, the consent form will state that participants have the option to opt out of DNA collection, and to request that their samples are destroyed at any time during the study. Participants will not receive any feedback from any of the genetic tests from study staff.

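### No structured side-effect inquiry is scheduled after alcohol at either laboratory visit, and the second treatment period lacks the pre-treatment one that the first has

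*Combined protocol and SAP*

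**What the plan says.** The baseline measures paragraph introduces the instruments: "During the medication phases, side effects will be assessed with the" SAFTEE and an adverse-event checklist. The paragraph on Follow-up Visits 1 and 2 places the side-effect assessment after the observed morning pill, the first smoking break and a snack, within "self-report and computerized assessments, including interim assessments of substance use and craving, side effects and adherence, and computer-based impulsivity tasks". The medical assessment comes next, and only then the alcohol: "Assuming no medical contraindications, participants will proceed to begin a previously validated alcohol self-administration procedure".

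Table 1 agrees. In both follow-up blocks SAFTEE/Adverse Effects Checklist appears once, above the row "Priming drink + absorption". The rows below that one are smoking-urge, alcohol-effect, alcohol-urge and drug-effect questionnaires, then the two purchase tasks and smoking breaks. The washout block, described as "7 days with no medication", lists a drinking calendar, dispensing of the second supply and an appetite questionnaire. The table ends with visit 2.

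Other sections provide some capture:

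- The Drug Effects Questionnaire gains medication-related items, with tiredness and nausea as examples (Alcohol administration session Questionnaires).
- Physiological and breath-alcohol readings are taken at 60, 90 and 120 minutes (Alcohol self-administration protocol).
- Staff are present throughout the alcohol sessions (Risks Related to Alcohol Administration Sessions).
- Staff report adverse events to the principal investigator within 24 hours (Unanticipated Problems/Adverse Events).
- A morning web survey asks about the previous day's drinks, side effects and adherence (Medication Schedule and Safety Monitoring).

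**The concern.** The laboratory session is the one occasion when drug and alcohol are taken together under controlled, measured conditions, and the structured side-effect interview is over before it begins. The risk section itself says that "it is possible that participants may experience dizziness/nausea from drinking during these visits, or during smoking breaks". It also reports dizziness (8.5% against 3.8% on placebo) and nausea (8.3% against 5.3%) among the commoner effects of lorcaserin in the obesity trials, so the two sources of symptoms overlap.

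The background names "the ability to quickly generate initial data on drug tolerability in the clinical population of interest" as an advantage of laboratory trials and states that no human trial has examined this drug class on alcohol consumption. The analysis section plans mixed models of tolerability and side-effect profiles by condition. As scheduled, that comparison would have no full-range adverse-event inquiry covering the session or the hours after discharge.

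The crossover adds a problem of attribution. If an event from visit 1 or the washout is first asked about in the second medication phase, it may be counted under the wrong pill.

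**Working it through.** The plan gives no figure to reproduce. The check sets the schedule out in order and counts days.

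**1. Where SAFTEE/checklist is listed.** Days are nominal: first phase Days 1 to 7, washout Days 8 to 14, second phase Days 15 to 21.

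| Occasion | Listed? |
|---|---|
| Baseline, before the first pills | Yes (10 min) |
| First-phase calls, Days 2 and 4 | Yes |
| Visit 1, Day 7, before alcohol | Yes (8 min) |
| Visit 1, after priming or ad libitum drinking | No |
| Washout and second dispensing | No |
| Second-phase calls, Days 16 and 18 | Yes |
| Visit 2, Day 21, before alcohol | Yes (8 min) |
| Visit 2, after alcohol, or any later day | No |

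**2. Gap after visit 1.** The call on day 2 of the second phase falls on Day 7 + 7 + 2 = 16. The gap is 16 − 7 = 9 days. The protocol allows slight departures from the 7-day intervals, so this is approximate. After visit 2 there is no later SAFTEE.

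**3. Sessions affected.** The Target Population section gives a final sample of 42; the power paragraph works with 34 after attrition from 42 randomised. That means 34 to 42 lorcaserin sessions, and as many placebo sessions, with no later SAFTEE on the same day. If the counterbalancing is equal, half of those participants (17 to 21) receive lorcaserin second and have no SAFTEE at all after their lorcaserin session. The other half are next asked about 9 days later.

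**4. Period baselines.** Period 1 has a SAFTEE before any pill is taken. Period 2 does not: its first SAFTEE is the day 2 call, when the other pill has already started. A symptom that began at visit 1 or in the washout has no earlier structured record to separate it from a new one.

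**5. What the other sources cover.**

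- *Added questionnaire items.* Table 1 lists the Drug Effects Questionnaire after the prime and after the ad libitum period. It solicits some symptoms under alcohol. It is a rating scale rather than an adverse-event interview, the protocol notes that not every questionnaire is given at every time point, and it ends before discharge.
- *Vital signs, breath alcohol and staff presence.* These rest on physiology and observation, and stop at discharge.
- *Morning survey.* It is described within the 7-day medication schedule, with no stated stop day. A survey on the morning after a laboratory visit would cover the session, but the text does not say that one is sent.
- *Side-effect calls.* These are limited to the two medication phases.

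**The case against.** The strongest reply is that a reader might infer that adverse events under lorcaserin plus alcohol are not systematically collected at all, and that this would be wrong. It would be. Participants are heavy drinkers by entry criterion, and the only abstinence instruction attached to the laboratory visits is for the preceding 24 hours. In each medication week the morning survey asks about drinks, side effects and adherence together, and SAFTEE follows by telephone on days 2 and 4 and again at the laboratory visit. Drinking at home on the study drug is therefore covered by structured inquiry. Within the session, nausea is one of the solicited items. That part of the reply stands and limits the point.

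A reader might also infer that SAFTEE is mistimed against the drug's peak, since "lorcaserin reaches peak plasma concentrations in 90 - 120 minutes after oral dosing". Summing the Table 1 rows after the pill gives 36 minutes to the end of SAFTEE and another 72 to the priming drink, 108 in all. Row order is not a clock, though. The sum omits an untimed snack and the physiological readings before the prime, and just over 12 further minutes would take the drink past 120. With twice-daily dosing and steady state after 3 days, the Day 7 interview already looks back over repeated peaks. Nor do the documents support a fixed number of hours of unobserved residual exposure after the last pill: they give a half-life of roughly 11 hours but no rule for how many half-lives to follow.

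Other replies have some weight. Silence about the survey's last day is not proof that it stops. The attached data and safety monitoring plan is not in the public text and could say more. Neither aim concerns safety, medication order is in the model, and staff see participants at the refill visit. None of this puts a structured inquiry after the alcohol or supplies a period-2 baseline.

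**Conclusion.** The point holds in limited form. At both visits the structured side-effect instrument is scheduled only before alcohol, no inquiry after discharge is specified, and period 2 lacks the pre-treatment SAFTEE that period 1 has. The gap covers the laboratory session, its aftermath and the period-2 baseline: 34 to 42 lorcaserin sessions, with about 9 days to the next SAFTEE after visit 1 and none after visit 2. Misattribution of washout events is possible under this schedule; its frequency cannot be estimated from the documents.

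The conclusion assumes that Table 1 is followed as written, that the morning survey does not run on the day after a visit, and that the unseen monitoring plan adds nothing. It does not affect the primary analysis of drinks consumed. It is a change worth making because it is cheap and bears directly on the planned tolerability comparison.

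**What to change.** Keep the existing SAFTEE slot, and:

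1. Repeat the Adverse Effects Checklist before discharge at both laboratory visits, during the monitored recovery wait.
2. State that the daily survey is sent on at least the morning after each laboratory visit, including visit 2.
3. Add SAFTEE/checklist to the second dispensing visit, before the pills are handed over.
4. In the analysis section, say which records feed the tolerability models, and report post-alcohol events separately from those of the medication week.

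A closing call after visit 2 is optional.

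The cost is about 8 minutes at each laboratory visit and 10 at the refill visit: 2 × 8 + 10 = 26 minutes per participant, against the stated 20 to 25 hours of participation, plus a few automated survey links. The refill visit has room: its Table 1 rows total 10 + 10 + 2 = 22 minutes of a 1-hour visit. Table 1 and the protocol wording change; dosing, the alcohol procedure and clinical management do not.

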**Table 1. Study Measures**

VISIT	MEASURE/PROCEDURE	TIME (MINS)
Screening	Consent	30
	Breath alcohol test	2
	Urine drug screen	5
	Urine pregnancy test (females)	5
	Expired CO	2
	TLFB	30
	SCID	60
	CIWA	5
	The Wechsler Test of Adult Reading (WTAR)	10
	Blood draw	5
Medical screen (may occur on different day than screening)	Physical Exam	10
	Medical History	15

VISIT	MEASURE/PROCEDURE	TIME (MINS)	
depending on availability)	EKG	20	
	CIWA	5	
Baseline/First Dispensing Visit	Demographics form	5	
	Locator form	10	
	CIWA	5	
	AUDIT	2	
	SRE	2	
	FTND	1	
	NDSS	3	
	TLFB	10	
	PACS	1	
	TQSU	1	
	Yale Craving Scale	5	
	Contemplation Ladder	1	
		Three Factor Eating Questionnaire	3
		Simplified Nutritional Appetite Questionnaire	2
		Reward Based Eating Drive Scale	2
		PROMIS Depression/BDI-II	4
		Stop signal	10
		CPT	10
		Reward Responsiveness Test	15
		Monetary Choice Questionnaire	2
		Alcohol Purchase Task	2
		Cigarette Self-efficacy (SEQ)	1
		Alcohol self-efficacy (AASE)	1
		Cigarette Purchase Task	2
		Inventory of Drinking Situations (IDS-30)	5
		Food delay discounting task	4
	SAFTEE	10	
Between Baseline & Follow up visit 1	Call participant on days 2 and 4 to assess side effects SAFTEE/Adverse Effects Checklist	10	
Follow up visit 1 (including alcohol consumption session)	Expired CO/Breath Alcohol	4	
	CIWA	5	
	Yale Craving Scale	5	
	Blood draw	5	
	Take dose of medication	2	
	Smoking break	15	
	TQSU	1	
	MNWS	1	

VISIT	MEASURE/PROCEDURE	TIME (MINS)
	PACS	1
	TLFB	10
	SAFTEE/Adverse Effects Checklist	8
	Cigarette Self-efficacy (SEQ)	1
	Alcohol self-efficacy (AASE)	4
	Stop signal	10
	CPT	10
	Reward Responsiveness Test	15
	Monetary Choice Questionnaire	2
	Alcohol Purchase Task	2
	Cigarette Purchase Task	2
	Food delay discounting task	4
	Weight	1
	Three Factor Eating Questionnaire	3
	Reward-Based Eating Drive Scale	2
	PROMIS Depression/BDI-II	4
	Simplified Nutritional Appetite Questionnaire	2
	Medical check-in	5
	Urine test (pregnancy, drugs, riboflavin)	5
	Priming drink + absorption	35
	TQSU	1
	BAES	1
	AUQ	1
	DEQ	1
	Ad libitum drinking session	120
	Smoking break	15
	TQSU	1
	BAES	1
	AUQ	1
	DEQ	1
	Alcohol Purchase Task	2

VISIT	MEASURE/PROCEDURE	TIME (MINS)
	Cigarette Purchase Task	2
	Smoking break	15
Washout	7 days with no medication	
	TLFB	10
	Dispense 2 nd medication	10
	Simplified Nutritional Appetite Questionnaire	2
Between Dispensing & Follow up visit 2	Call participant on days 2 and 4 to assess side effects SAFTEE/Adverse Effects Checklist	10
Follow up visit 2 (including alcohol consumption session)	Expired CO/Breath Alcohol	4
	CIWA	5
	Yale Craving Scale	5
	Blood draw	5
	Take dose of medication	2
	Smoking break	15
	TQSU	1
	MNWS	1
	PACS	1
	TLFB	10
	SAFTEE/Adverse Effects Checklist	8
	Cigarette Self-efficacy (SEQ)	1
	Alcohol self-efficacy (AASE)	4
	Stop signal	10
	CPT	10
	Reward Responsiveness Test	15
	Monetary Choice Questionnaire	2
	Alcohol Purchase Task	2
	Cigarette Purchase Task	2
	Food delay discounting task	4
	Weight	1
	Three Factor Eating Questionnaire	3

VISIT	MEASURE/PROCEDURE	TIME (MINS)
	Reward Based Eating Drive Scale	2
	PROMIS Depression/BDI-II	4
	Simplified Nutritional Appetite Questionnaire	2
	Medical check-in	5
	Urine test (pregnancy, drugs, riboflavin)	5
	Priming drink + absorption	35
	TQSU	1
	BAES	1
	AUQ	1
	DEQ	3
	Ad libitum drinking session	120
	Smoking break	15
	TQSU	1
	BAES	1
	AUQ	1
	DEQ	1
	Alcohol Purchase Task	2
	Cigarette Purchase Task	2
	Smoking break	15

VI. *Anticipated End Date*

We anticipate completing all data collection by March of 2021. At the time of study closure, after all follow-up data have been collected, all participant identifiers (name, address, etc.) will be made inaccessible to the research team. MRN retains the link between identifiers and URSI indefinitely for the potential future benefit to the research participant. Specifically, it may become medically advantageous in the future for a former participant to have access to the clinical information that may be present in the medical screening.

VII. *Project Location(s)*

All study procedures and participant interactions will take place at the Mind Research Network.

